13.4 Hypothesis Tests

13.4.1 Primary Hypotheses

The primary study hypothesis (alternative hypothesis) is that Ketamine and experimental drug NRX-101 (K/N) delays the time to documented relapse as compared to both lurasidone (L) and placebo (P) as measured by the hazard ratio (h) versus the null hypothesis of no delay in time to relapse for either comparator treatment (Ketamine/lurasidone [K/L] and Ketamine/placebo [K/P]) as follows:

- H₀: $h_{\text{NRX-101}} < h_L$ and h_P
- H_a: $h_{\text{NRX-101}} > h_L$ and h_P

13.4.2 Secondary Hypotheses

The secondary study hypotheses relating to secondary ASIB and BPD endpoints (alternative hypotheses favoring K/N vs. K/L and K/P) are the following:

1. K/N will favorably separate from both K/L and K/P by 72 hours, with sustained difference between groups thereafter.
2. All cause discontinuation (including discontinuation for continued suicidal ideation) will be lower for K/N than both K/L and K/P.
3. K/N will favorably separate from K/L and K/P starting at day 7, with sustained difference thereafter.
4. Improvements within the K/N group observed at Week 2 will remain stable to end of study.
5. C-SSRS scores will remain <4 for 4 weeks following treatment discontinuation (i.e. any “crisis” will resolve within the 6 week time period with more favorable outcomes in the K/N group as compared to K/L and K/P).

13.5 Efficacy Endpoints

13.5.1 Primary Efficacy Endpoint

The primary outcome measure will be time to relapse, defined as the need to implement a new treatment plan (not a dose increase, decrease, or suspension) or as a return to a score of ≥ 4 on the C-SSRS, and/or a score of 20 on the MADRS subset of the BISS

13.5.2 Secondary Efficacy Endpoints

Additionally, symptom improvement will be evaluated by assessing changes in the secondary outcome measures: C-SSRS, CHRT, BISS (MADRS), and BPRS. These measures will be assessed at the times specified on the Study Activity Schedule, Table 3.

The C-SSRS (and the retrospective C-CASA component), CHRT (CHRT-SR and CHRT-C), BISS and BPRS (including the global severity rating) will be evaluated within and between study

treatment groups. The time frame is for both lifetime and the past six months for the Baseline/Screening scale and since the last visit for the Since Last Visit scale. Mean differences will be evaluated using a paired t-test with each study group and an unpaired t-test for K/N vs. K/L and K/P.

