MDL100907/GV150526A	2 mpk	MDL100907	0.3 mpk	GV150526A	—	11	20.818	16.8459	863.55	93.861
MDL100907/L701324	2 mpk	MDL100907	0.3 mpk	L701324	—	10	25.980	31.5739	622.90	189.097
MDL100907/PCP	2 mpk	MDL100907	0.3 mpk	PCP	1 mpk	10	14.916	13.8546	792.60	155.336
Ketanserin	2 mpk	Ketanserin	2 mpk	—	—	10	10.400	11.0660	648.90	161.515
Ketanserin/D-cycloserine	2 mpk	Ketanserin	2 mpk	D-cycloserine	300 mpk	10	21.390	18.2661	640.60	96.388
EMD281014	2 mpk	EMD281014	30 mpk	—	—	10	23.050	20.7267	628.20	110.375
EMD281014/D- cycloserine	2 mpk	EMD281014	30 mpk	D-cycloserine	300 mpk	10	27.380	26.7496	541.10	148.076
Antipsychotics										
Lurasidone	2 mpk	Lurasidone	1 mpk	—	—	10	36.020	16.2589	715.50	116.712
Lurasidone/D-cycloserine	2 mpk	Lurasidone	1 mpk	D-cycloserine	300 mpk	10	53.230	17.6298	739.10	91.594
Quetiapine	2 mpk	Quetiapine	30 mpk	—	—	10	8.950	10.6937	676.50	116.319
Quetiapine/D-cycloserine	2 mpk	Quetiapine	30 mpk	D-cycloserine	300 mpk	10	26.004	28.9504	630.20	140.271
Antidepressants										
Duloxetine	2 mpk	Duloxetine	10 mpk	D-cycloserine	300 mpk	10	22.290	30.4841	979.50	181.190
Mirtazapine	2 mpk	Mirtazapine	5 mpk	D-cycloserine	300 mpk	10	25.282	22.3245	764.20	97.790
Vanlafaxine	2 mpk	Vanlafaxine	16 mpk	D-cycloserine	300 mpk	10	21.144	12.0805	928.50	78.921

Source: [Javitt, 2014](#)

[figure not shown]
Our preclinical research, using the Rat Akathisia model, suggests an additional synergistic interaction between DCS and lurasidone. On one hand, as described above, DCS appears to block the anxiogenic effects of lurasidone. Conversely, lurasidone may in turn have the ability to reverse low-level psychotomimetic effects of DCS and ketamine. This signal may be appreciated from the decrease in distance traveled when lurasidone is added to DCS. Lurasidone mediates its antipsychotic effects at both D2 and 5-HT2A receptors. As opposed to pure serotonergic agents used in the treatment of major depressive disorders (e.g., SSRIs), the additional D2 blockade of lurasidone makes it a clinically effective antipsychotic and, thus, also potentially effective in treatment of psychotic symptoms that may be induced by NMDA antagonists.

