8.1.4 Stage 1: Ketamine Infusion

For entry into Stage 1 of the study (ketamine infusion), all eligibility criteria MUST continue to be met (i.e., all inclusion criteria and no exclusion criteria).

All subjects will receive ketamine by continuous infusion for 40 minutes by use of an electronic pump. The start and stop times of the ketamine infusions will be documented in the eCRF.

Detailed instructions for dose preparation will be provided to site research pharmacists in an additional guidance document. Storage conditions should be followed according to the package insert. Dosing procedures will be provided to the clinical unit in a separate infusion document.

Assessments: During the infusion, the Clinician Administered Dissociative Symptom Scale (CADSS) and the Brief Psychiatric Rating Scale (BPRS) are administered at 0 (-5 minutes), 40 minutes (completion of infusion) and 4 hours. Both are administered by a clinician.

Physiological Monitoring: Each participant will be allowed to rest in a semi-recumbent position. Each subject will receive an intravenous (IV) line. The monitoring will include a non-invasive blood pressure cuff, a 3- or 5-lead ECG, a pulse oximeter and oxygen by face mask or nasal cannula at 4 to 6 liters per minute, as needed. Vital signs will be monitored continuously and recorded every 20 minutes. Each subject will receive an infusion for 40 minutes.

The IV line will be left in place for at least 1 hour following the infusion to allow for additional medications to control emergent side effects. Medical staff monitoring the infusion will be prepared to treat increases in blood pressure greater than 180/100 mmHg or heart rate greater than 110 bpm, or follow their institutional guidelines if more conservative. If these elevations resolve spontaneously within a short time period, they will generally not be treated. The study

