8.2.5.2.2. Safety Measures

The Patient Rated Inventory of Side Effects (PRISE), CADSS, and Barnes Akathisia Scale (BARS) (including the global severity rating) will be evaluated within and between study treatment groups. Mean changes from baseline for the differences from baseline and after randomization baseline will be evaluated using a paired t-test within each study group and an unpaired t-test for K/N vs. K/L and K/P.

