11. ASSESSMENT OF EFFICACY

The primary outcome measure will be time to relapse, defined as a return to a score of ≥ 4 on the C-SSRS, and/or a score of 20 on the MADRS subset of the BISS. The RAC will adjudicate each site reported instance of relapse for compliance the protocol definition of time to relapse.

Relapse is a time-to-event outcome reflective of this multi-component disorder. Time to relapse is more sensitive measure than an assessment at a fixed time. Time to relapse will be displayed using a Kaplan-Meier lifetable with the treatment groups compared using a two-sided Wilcoxon-Gehan test and a proportional hazard model to include the above cited covariates.

Titration of DCS or lurasidone within the dosing range will not be considered to be a relapse.

All of the instruments used to measure ASIB or depression constitute serial continuous and ordinal outcomes which will be analyzed using MMRM, which accounts for missing data and early discontinuations. These instruments include the following:

- C-SSRS (and the retrospective C-CASA component)
- CHRT (CHRT-SR and CHRT-C)
- BISS
- SIBQ
- BPRS

The models will include treatment group, study visit, the interaction between study visit and treatment group, the baseline of the variable being analyzed, C-SSRS 24 hours post infusion (1, 2), age (<25 yrs, 25-39 yrs, >40 yrs), and gender as fixed effects. The reason for missing data will be evaluated as a condition of MMRM analysis.

Means, mean changes, standard deviations, and ranges will be presented separately for Stage 1 and then for each Stage 2 treatment group over time. These endpoints will be evaluated within the three study treatment groups for the change from Stage 1 and Stage 2 baselines using a paired t-test and between study treatment groups using an unpaired t-test at each time; these p-values will be presented as descriptive statistics.

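### BPRS and CADSS are to be compared between randomised arms, but both are rated only around the ketamine infusion, before randomisation, so the comparisons cannot show an effect of NRX-101

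*Combined protocol and SAP*

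**What the plan says.** **Planned analyses, BPRS.** Section 13.5.2 says "BISS and BPRS (including the global severity rating) will be evaluated within and between study" treatment groups, and then: "Mean differences will be evaluated using a paired t-test with each study group and an unpaired t-test for K/N vs. K/L and K/P". Section 8.2.5.1.2 plans the same t-tests. Section 11 states "All of the instruments used to measure ASIB or depression constitute serial continuous and ordinal outcomes which will be analyzed using MMRM", and its instrument list includes BPRS. The model there has treatment, visit and treatment-by-visit terms. Section 13.10.6 refers back to that list, and Section 13.10.4 makes the MMRM in the ITT population the primary analysis of the secondary efficacy endpoints.

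**Planned analyses, CADSS.** Section 8.2.5.2.2 lists "CADSS, and Barnes Akathisia Scale (BARS) (including the global severity rating) will be evaluated within and between study treatment groups", by paired and unpaired t-tests. Section 13.7.2 repeats this.

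**Rating times.** Section 13.5.2 ties the secondary measures to the schedule: "These measures will be assessed at the times specified on the Study Activity Schedule, Table 3". Table 3 marks BPRS and CADSS in two columns only, ketamine dosing and 4 hours. Section 8.1.4 says that both scales "are administered at 0 (-5 minutes), 40 minutes (completion of infusion) and 4 hours". Section 8.2.6.2 gives different CADSS times (-5, 40, 80 and 120 minutes), all on infusion day.

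**Randomisation.** Sections 8.1.6 and 8.2.3 and Table 3 place it after the response check 24 hours post infusion, on Day 1. Section 4.6 starts the oral drug on Day 1.

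**The concern.** A score recorded before assignment cannot be changed by assignment. If every BPRS and CADSS rating precedes randomisation, the planned arm comparisons hold no information about NRX-101.

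This matters because the plan gives reasons to want that information. The synopsis names both scales among the means of assessing NRX-101 safety and tolerability. Section 4.4 argues that "lurasidone may in turn have the ability to reverse low-level psychotomimetic effects of DCS and ketamine", which accepts that DCS may have such effects. Section 4.6 sets the goal of an oral agent without ketamine's potential for psychosis. Section 8.2.5.2.3 notes that only 21 subjects have received DCS 1000 mg in formal psychiatric studies. A table showing no arm difference on BPRS or CADSS could be read as randomised evidence that NRX-101 causes no psychotic or dissociative symptoms, and it would be no such evidence.

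**Working it through.** **1. Where the ratings fall.** The Ketamine Infusion and Randomization rows of Table 3 fix the positions of the dosing and Day 1 columns. Reading the other rows against them:

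| Scale | Marked before randomisation | Marked at Day 1 (24 h) | Marked Days 7 to 42 |
|---|---|---|---|
| BPRS | dosing, 4 h | none | 0 of 7 visits |
| CADSS | dosing, 4 h | none | 0 of 7 visits |
| BARS | dosing | none | 7 of 7 visits |
| BISS | screening, dosing, 4 h | yes | 7 of 7 visits |

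BARS stands beside CADSS in the analysis sections and is marked at every visit from Day 7 to Day 42. The blank cells for BPRS and CADSS are therefore not a fault of the whole table.

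**2. Gap to randomisation.**
- Last rating under Section 8.1.4: 24 − 4 = about 20 hours before randomisation.
- Last CADSS rating under Section 8.2.6.2 (120 minutes): 24 − 2 = about 22 hours before.
- If the response check came at the early limit of the Stage 1 per-protocol window in Section 6.4 (18 hours): 18 − 4 = 14 hours before.

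No reading of the documents puts a rating after assignment and on treatment.

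**3. What the t-test does with such scores.** Inputs are 56 K/N against 28 K/L (or 28 K/P) evaluable subjects (Section 13.8.3) and two-sided alpha 0.05 (Section 13.9). With a true difference of d standard deviations, the normal approximation to power is Φ(d × √[n₁n₂/(n₁+n₂)] − 1.96), where √(56 × 28 / 84) = 4.32.

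- Check against the plan's own figure: Table 13 gives 90% power at d = 0.754. Here 0.754 × 4.32 = 3.26, 3.26 − 1.96 = 1.30, and Φ(1.30) = 0.903. It reproduces.
- Pre-randomisation score: d = 0 by design. The two-sided rejection probability is 2 × Φ(−1.96) = 0.050. A simulation of the t-test with 56 against 28 subjects and 20,000 runs gave 0.049.

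So the test rejects at its nominal level however large or small the effect of NRX-101 on these symptoms.

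**4. What cannot be computed at all.** Sections 8.2.5.1.2 and 8.2.5.2.2 also call for change from a baseline after randomisation. Neither scale is rated at 24 hours or at any on-treatment visit, so that change does not exist. For the BPRS MMRM there is no Stage 2 visit to supply the treatment-by-visit term.

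**The case against.** The strongest reply is that this is a leftover list entry with little consequence.

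- Sections 11 and 13.10.3 call the visit-wise t-test p-values descriptive. Neither scale is in the primary endpoint (13.5.1), the numbered secondary hypotheses (13.4.2) or the testing hierarchy (13.9). This stands: the trial's formal error rate is not at stake, and the 5% figure describes an uninformative test, not a threatened claim.
- Other text suggests a drafting slip. Section 5.2 and the first paragraph of 8.2.5.1.2 omit BPRS from the secondary measures. Section 8.2.6.2 defines CADSS change over infusion-day times only. The reference to a global severity rating, attached to BPRS in 13.5.2, belongs to BARS elsewhere. This is plausible, but it explains the error without removing it.
- Psychotomimetic events would not go unseen. Adverse events are collected at every Stage 2 visit, PRISE is completed on Day 1 and Days 7 to 42, Section 8.2.5.2.3 requires daily clinician contact, and the DSMB reviews adverse events every 4 months. This stands too: what is missing is a scaled, clinician-rated comparison, not surveillance.
- In the copy of Table 3 available to us, the Day 70 column has no mark in any row, although Section 8.1.7 refers to Day 70 procedures. A lost mark cannot be excluded. It would fall four weeks after treatment ends, and Sections 8.1.4 and 8.2.6.2 name infusion-day times only, so it would not supply on-treatment data.

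These points limit the seriousness. None supplies an on-treatment rating.

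**Conclusion.** The concern holds. The between-arm analyses of BPRS and CADSS rest wholly on data collected before randomisation: zero scheduled on-treatment values in all 124 randomised subjects, no power for an NRX-101 effect, and a requested post-randomisation change score that cannot be derived. The plan should be corrected, but the primary endpoint and the hierarchy are untouched.

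Two assumptions apply. First, Table 3 and Section 8.1.4 are followed as written; Section 13.5.2 itself defers to Table 3, so unlisted later ratings should not be presumed. Second, the arms are compared as randomised. The Stage 2 ITT set requires study treatment and a post-baseline efficacy assessment, so differential exclusions could produce an arm difference by selection. That would still not be an effect of NRX-101 on either scale.

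**What to change.** Choose one of two courses.

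1. **Collect the data.** Add the 4-item BPRS positive-symptom subscale (the only part of BPRS used, per Section 8.2.6.1) at the 24-hour visit before the first oral dose, as baseline, and at the Stage 2 visits where BISS is already rated (Days 7, 10, 14, 21, 28, 35 and 42). That is 1 + 7 = 8 ratings per completer. Do the same for CADSS (23 items) if it is to remain a between-arm measure. The cost is a schedule amendment and rater time at existing visits; the documents give no administration time. Only this course yields randomised data on psychotic symptoms.

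2. **Drop the comparisons.** Remove BPRS from the between-arm lists in Sections 8.2.5.1.2, 11, 13.5.2 and 13.7.2 (13.10.6 follows from 11), and CADSS from 8.2.5.2.2 and 13.7.2. Report both as change during Stage 1, and amend the synopsis so that it no longer presents them as measures of NRX-101 safety. The cost is wording, in protocol as well as statistical sections.

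Under either course, reconcile the CADSS times in Sections 8.1.4 and 8.2.6.2, and correct the global severity wording attached to BPRS in 13.5.2.

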13.5.3 Diagnostic Metrics

The following metrics will be evaluated at baseline:

- MINI 7.0.2

13.6 Additional Endpoints

The following additional endpoints will be recorded and analyzed for both study phases:

- Study dose per treatment group
- All-cause discontinuation (and reason for discontinuation)
- Suicide rates
- Incidence of hospitalization and ER visits for disease-related outcomes
- Proportion of subjects who are treated with new SSRIs or have increased SSRI dosages
- Proportion of subjects who discontinue SSRIs or have reduced SSRI dosages.

13.7 Safety Endpoints

13.7.1 Overall Adverse Events

Separate safety analyses will be performed for the two stages for the Safety population. Safety endpoints will include adverse events (AE), vital signs (VS), and relevant clinical chemistries and hematology parameters.

The principle of treatment emergence will be employed for the analysis of AE data. Treatment emergence is defined to be any event that occurred during the observation period and was not present at baseline, or one which represents an exacerbation of a condition present at baseline.

Events emerging during Stage 1 will be counted during Stage 2 if not resolved by the start of randomized treatment initiation. Unresolved adverse event outcomes at the end of Stage 2 will be followed for an additional seven days or until resolution, whichever occurs earlier.

Adverse events will be classified by MedDRA. For each study treatment, safety data will be collected and analyzed per stage or until treatment-emergent adverse events are resolved. The type, incidence, timing (onset, duration), relationship, and severity of AEs will be reported for

treatment-emergent and SARs. Reasons for withdrawal due to AEs will also be reported. Narratives will be written for every AE classified as serious or associated with death. Safety results will be displayed separately for each stage and combined.

Safety and tolerability will be assessed using two-sided Fisher Exact tests to compare K/N vs. K/L and K/P. Mean changes from baseline will be displayed for each serum chemistry and hematology parameter as well as the shift; unpaired t-tests will be used to compare K/N vs. K/L and K/P; in addition, paired t-tests will be performed for the change from baseline for each study treatment group.

13.7.2 Other Safety Measures

The study is being conducted in a population who would likely have been admitted to a psychiatric hospital, if they did not have a positive response to ketamine. Moreover, it is expected that some subjects in the K/L and K/P treatment groups will have recurrence of their depression and, possibly suicidality. The timing and incidence of adverse findings will be compiled following planned surveillance of all study subjects by a designated safety monitor. The number of such episodes will be evaluated using a Poisson regression model to compare study treatment groups controlling for C-SSRS 24 hours post infusion (1, 2), age (<25, 25-39, ≥40), and gender.

Vital signs and ECGs will also be evaluated within and between study treatment groups. Mean differences in heart rate, QRS duration, PR interval, RR interval, QT, and QTcF. QTcF intervals will be calculated using the Fridericia formula (Puddu et al, 1988). The overall interpretation will be reported as normal or abnormal; if abnormal, then the percents clinically significant will be reported. Abnormal values shall not be recorded as AEs unless deemed clinically significant. McNemar paired comparison tests will be performed within study treatment groups for the abnormal percents while Fisher Exact tests will be performed between treatment groups.

While symptom improvement will be evaluated by assessing changes in the secondary outcome measures: C-SSRS, CHRT, BISS (MADRS), SIBQ and BPRS, safety measures in the PRISE, CADSS and BARS (including the global severity rating) will be evaluated within and between study treatment groups. The time frame is for both lifetime and the past six months for the Baseline/Screening scale and since the last visit for the Since Last Visit scale. Mean differences will be evaluated using a paired t-test with each study group and an unpaired t-test for K/N vs. K/L and K/P.

